MTD	maximum tolerated dose
NCI	National Cancer Institute
OxyHb	oxyhemoglobin
PD	pharmacodynamic
PE	physical examination

Abbreviation	Definition
PGI-C	Patient Global Impression of Change
PK	pharmacokinetic(s)
QTcF	QT interval corrected using Fridericia's formula
RBC	red blood cell
RSI	Reference Safety Information
SAE	serious adverse event
SCD	sickle cell disease
SMC	Safety Monitoring Committee
SUSAR	suspected unexpected serious adverse reaction
TEAE	treatment-emergent adverse event
ULN	upper limit of normal
US	United States
VOC	vaso-occlusive crisis
WBC	white blood cells

PROTOCOL SYNOPSIS

Study Number	GBT440-029
Study Title	An Open Label, Multiple Dose Escalation Study to Evaluate the Safety, Tolerability, Pharmacokinetics, and Pharmacodynamics of Voxelotor in Patients with Sickle Cell Disease
Investigational Product	Voxelotor tablets, 500 mg tablets administered orally
Sponsor	Global Blood Therapeutics, Inc. [name] United States of America
Number of Clinical Sites	The study will be conducted at up to approximately 10 clinical sites.
Number of Study Participants	Up to 40 participants.
Treatment	Voxelotor will be supplied as 500 mg tablets and will be administered at doses ranging from 1500 mg to up to 3000 mg.
Objectives	
Primary Objective:
 
• To evaluate the tolerability and safety of voxelotor at daily doses of > 1500 mg (2000 mg to 3000 mg) in participants with sickle cell disease (SCD) 
Secondary Objectives:
 
• To evaluate the change in hemoglobin (Hb) and hemolysis measures• To evaluate the incidence rate of vaso-occlusive crises (VOCs) 
Exploratory Objectives:
 
• To evaluate the PD properties (effect on Hb-oxygen equilibrium curve [OEC]) as measured by P50 and P20• To assess voxelotor pharmacokinetics (PK) as evaluated by population PK analysis and % Hb occupancy• To evaluate the PK-PD relationship of voxelotor at daily doses of >1500 mg• To evaluate the effects of voxelotor on Clinical Global Impression of Change (CGI-C) and Patient Global Impression of Change (PGI-C)
Study Design	This is an open-label, sequential period, within-participant dose escalation study. Up to 40 participants with SCD (HbSS or HbSB ⁰) who are 18 to < 60 years of age, inclusive, will be enrolled.

Study Design (continued)	
Study participants will undergo up to four periods of voxelotor administered orally at progressively higher dose levels from 1500 mg until either a maximum tolerated dose (MTD) or 3000 mg/day dose is reached, whichever occurs first:
 
• Period 1: 1500 mg per day: 1500 mg once daily (3 × 500 mg tablets) for 3 weeks (± 3 days)• Period 2: 2000 mg per day: 1000 mg (2 × 500 mg) twice daily (BID) for 3 weeks (± 3 days)• Period 3: 2500 mg per day: 1500 mg (3 × 500 mg) in morning and 1000 mg (2 × 500 mg) in evening daily for 3 weeks (± 3 days)• Period 4: 3000 mg per day: 1500 mg (3 × 500 mg) BID for 3 weeks (± 3 days)• Observation Period: MTD or 3000 mg daily for 24 weeks• Safety Follow-up Period: from day of last dose to 28 days postdose. 
If at any time a dose level > 1500 mg is not tolerated by a participant, the dose may be reduced to a previous level for the participant, which will then be administered for 24 additional consecutive weeks as an observation period.
 
Dose modifications are allowed during the observation period in consultation with the Sponsor's Medical Monitor.
 
If 1500 mg daily is the MTD for a participant, then the participant may enter the observation period and continue to receive 1500 mg for up to 24 weeks until such time as they are able to roll over into the open-label extension study or receive commercial voxelotor, where available. If the participant discontinues early from the study, the participant will undergo an End of Study (EOS) visit approximately 28 days after the last dose and will not be eligible for the open-label extension study.
 
The safety of study participants will be closely monitored by the study team. In addition, a Safety Monitoring Committee (SMC) will review safety, tolerability, and available PK and PD data at regular intervals. Blood draws for PK and PD (including Hb and hemolysis markers), routine chemistry and hematology laboratory tests, and 12-lead electrocardiograms (ECGs) in triplicate will be obtained periodically as listed in the Schedule of Assessments.
 
Upon completion of the observation period for individual participants or after study termination, eligible participants will be given the option to enroll in an open-label extension study.

Duration of Study Participation	Study participation will be for up to 44 weeks, which includes up to 30 days in Screening Period; 21 days (3 weeks) each in Periods 1, 2, 3, and 4; 168 days (24 weeks) in the Observation Period; and 28 days in the Safety Follow-up Period.
Statistical Methods	
Primary Endpoints
 
• Treatment-emergent adverse events (TEAEs) and serious adverse events (SAEs)

Statistical Methods (continued)	
Secondary Endpoints
 
• Change in Hb and clinical measures of hemolysis (unconjugated bilirubin, % reticulocyte, absolute reticulocyte, and lactate dehydrogenase [LDH]) from Baseline• Proportion of participants with an Hb increase > 1 g/dL compared to Baseline• Incidence rate of VOCs 
Exploratory Endpoints
 
• P50 and P20 at 8 hours and 24 hours postdose• PK of voxelotor as assessed by population PK analysis using nonlinear mixed-effect modeling• % Hb occupancy at 8 hours and 24 hours postdose• CGI-C• PGI-C 
Sample Size
 
As this is an exploratory study to provide descriptive information on the tolerability, safety and efficacy of voxelotor at dose levels > 1500 mg daily, the sample size chosen was based on previous experience in exploratory studies to support the assessment of a MTD based on descriptive summaries of safety and PK data. The sample size of up to 40 participants takes into account the differential tolerance in participants, some potentially tolerating 3000 mg daily, while others only tolerating lower dose levels. An effort will be made to enroll a number of subjects sufficient to ensure that at least 6 participants are treated at the study level MTD.
 
Populations for Analysis
 
Safety Population: All participants who receive at least one dose of study drug will be included in the safety population.
 
PK Population: The PK population will consist of all participants who receive any amount of study drug and have at least one measured concentration at a scheduled PK time point after the start of dosing.
 
Analyses
 
TEAEs, defined as events that occur on or after Day 1 of study drug or the worsening of a pre-existing condition on or after Day 1 of study drug, will be classified according to the Medical Dictionary for Regulatory Activities (MedDRA). The incidence of TEAEs and relatedness to study drug, as assessed by the Investigator, will be summarized descriptively by maximum dose level tolerated.
 
Clinical laboratory tests, ECGs, and vital signs over time will be summarized by maximum dose level tolerated using descriptive statistics.
 
An Hb responder endpoint, defined as an increase in Hb of > 1 g/dL compared to Baseline, will be summarized. Additionally, change from baseline in Hb and clinical measures of hemolysis (unconjugated bilirubin, % reticulocyte, absolute reticulocyte, and LDH) will be summarized by maximum dose level tolerated using descriptive statistics.
 
The incidence of VOCs will be summarized by maximum dose tolerated.

--	---

Statistical Methods (continued)	The CGI-C and PGI-C will be summarized by maximum dose level tolerated. Population PK analysis using nonlinear mixed-effect modeling will be performed to characterize voxelotor PK in plasma and whole blood.
--	--

1. INTRODUCTION

1.1. Disease Background

Sickle cell disease (SCD) is a rare and inherited disorder caused by a point mutation in the β -globin gene, leading to formation of hemoglobin S (HbS). It is a devastating and debilitating disease marked by the pathophysiologic features of hemolytic anemia, vaso-occlusion, and progressive end-organ damage, with a clinical course characterized by life-long disability and early death. A primary and obligatory event in the molecular pathogenesis of SCD is the polymerization of deoxygenated HbS, which leads to sickling of red blood cells (RBCs). The resulting hemolytic anemia is experienced to various degrees by all patients with SCD and is a defining and serious feature of the disease. Hemolytic anemia leads to reduced oxygen-carrying capacity, tissue hypoxia, and clinical manifestations of end-organ damage in patients with SCD. The disease course is also characterized by life-long pain and frequent healthcare interactions. Chronic hemolytic anemia, and its sequelae, have become the leading cause of mortality in adults with SCD and is recognized as a critical contributor to irreversible cumulative organ damage and dysfunction (Lanzkron, 2013; Vichinsky, 2018). Half of adult patients with SCD have irreversible organ damage, and presence of dysfunction in a single organ is an independent predictor of death and subsequent multiorgan dysfunction (Powars, 2005).

Hemoglobin (Hb) concentration is an important indicator of disease severity, indicating not only the degree of anemia but also the degree of hemolysis that occurs in patients with SCD, as evidenced by the strong inverse correlation between Hb and clinical measures of RBC destruction, such as indirect bilirubin, reticulocyte count, and lactate dehydrogenase (LDH), and the association of low Hb and elevated hemolysis with increased risk of mortality (Taylor, 2008). It is well established that low Hb levels are associated with an increased risk for end-organ complications in SCD, including stroke/silent cerebral infarction, chronic kidney disease, leg ulcers, and pulmonary hypertension (Powars, 1991; Ohene-Frempong, 1998; Gladwin, 2004; Ataga, 2018).

Therapies approved for the treatment of SCD in some regions include hydroxyurea (HU) (Smith, 2011), L-glutamine (Emmaus Medical, 2018), and crizanlizumab (Novartis, 2019). Hydroxyurea is an established therapeutic option that is indicated to reduce the frequency of painful crisis and the need for blood transfusions in patients with recurrent moderate-to-severe sickle cell crises (E.R. Squibb, 2018). L-glutamine is an approved therapy in the United States (US) that is indicated to treat the acute complications of SCD in adult patients and pediatric patients five years of age and older (Emmaus Medical, 2018). Although shown to decrease vaso-occlusive crises (VOCs), L-glutamine has no demonstrated effect on hemolytic anemia. Despite the current standard of care, patients with SCD continue to suffer serious morbidity and premature mortality (Steinberg, 2003). Crizanlizumab is approved in the US to reduce the frequency of VOCs in adults and pediatric patients aged 16 years and older with SCD (Novartis, 2019).

1.2. Voxelotor

Voxelotor (formerly known as GBT440) is an orally administered small molecule that inhibits HbS polymerization by allosterically modifying Hb-O₂ affinity and is being developed for the treatment of SCD. Voxelotor was designed to bind to HbS with preferential partitioning into RBCs. It binds covalently and reversibly via Schiff base to the N-terminal valine of the Hb

α chain (ie, a single voxelotor molecule binding per HbS tetramer in a 1:1 stoichiometry) and allosterically ([Eaton, 1999](#)) increases HbS-O₂ affinity ([Oksenberg, 2016](#)), stabilizing the oxyhemoglobin (oxyHb) state and inhibiting polymerization ([Oksenberg, 2016](#)). The voxelotor binding site is distant from heme pockets and therefore it can increase O₂ affinity without sterically blocking the release of O₂.

A primary and obligatory event in the molecular pathogenesis of SCD is the polymerization of deoxygenated HbS. Because oxyHb is a potent inhibitor of HbS polymerization, increasing the proportion of oxyHb in all RBCs with voxelotor can reduce HbS polymerization, decrease RBC membrane damage and destruction and has the potential to subsequently achieve long term disease modification. This principle is supported by the finding that in patients with sickle hereditary persistence of fetal hemoglobin (HbF), the dilution of HbS by 20% to 30% HbF in all RBCs is sufficient to inhibit HbS polymerization, preventing RBC damage and SCD clinical sequelae. This suggests that pharmacologically maintaining approximately 20% to 30% of Hb in the nonpolymerizing oxygenated state in all RBCs may be an effective approach for the treatment of SCD. This therapeutic effect was demonstrated in the pivotal Phase 3 study (GBT440-031) where 1500 mg of voxelotor, achieving Hb modification of 20% to 30%, administered daily orally for 24 weeks showed a significant and clinically meaningful increase in Hb, and decrease in hemolysis ([Vichinsky, 2019](#)).

In November 2019, the US Food and Drug Administration (FDA) approved voxelotor, now known by the trade name Oxbryta™, for the treatment of SCD in adults and pediatric patients 12 years of age and older. However, voxelotor remains an investigational drug outside of the US, and this study administers doses at and higher than the approved dose in the US.

1.3. Summary of Relevant Nonclinical Data and Clinical Data

1.3.1. Nonclinical Data

Primary pharmacodynamics (PD) studies of voxelotor consisted of in vitro and in vivo studies to characterize (a) voxelotor binding and affinity for Hb, (b) the effect of voxelotor on HbS modification using purified Hb, washed RBCs, and whole blood, and (c) the efficacy of voxelotor in vivo in a mouse model of SCD. These in vitro assays of increasing complexity included measuring Hb-O₂ via hemoxygometry, quantifying stabilization of the oxyHb state conformation, delaying HbS polymerization at low oxygen tension, preventing in vitro sickling induced by a low oxygen environment, decreasing viscosity, and improving deformability of RBCs in blood from patients with SCD ([Dufu, 2018](#)). In addition, these studies show that voxelotor-modified Hb retains the Bohr Effect, which is the ability to offload oxygen from Hb in metabolically active (low pH) tissues.

Collectively, these studies demonstrate that voxelotor increases Hb-O₂ affinity with high specificity of binding to Hb, stabilizes the oxy or R-state conformation of Hb, prevents HbS polymerization and RBC sickling in vitro, and improves sickle blood viscosity and deformability in vitro. In addition, voxelotor increases HbS-O₂ affinity and RBC half-life, while decreasing ex vivo sickling and reticulocyte count in a SCD mouse model.

Additional information regarding nonclinical pharmacology (including safety pharmacology and metabolism) and toxicology is provided in the most current version of the Voxelotor Investigator's Brochure (IB), provided separately.

1.3.2. Clinical Data

As of 05 November 2019, approximately 823 participants have received single or multiple doses of voxelotor in 23 clinical development studies (five studies in SCD, two studies in idiopathic pulmonary fibrosis [IPF], 15 clinical pharmacology studies, and one physiology study of healthy participants exercising in hypoxic conditions).

The 823 participants consist of:

- 379 participants with SCD (122 pediatric and 257 adult participants)
- 378 healthy participants (including participants with severe renal impairment [not on dialysis] and participants with hepatic impairment)
- 43 adult participants with IPF
- 23 participants from the expanded access program (6 adolescents and 17 adults)
 - 15 participants from the GBT-sponsored expanded access protocol
 - 8 participants from the single-patient Investigational New Drug (IND) program

Information regarding the safety, tolerability, and efficacy of voxelotor is provided in Section 1.4. and can be found in the Voxelotor IB.

1.4. Summary of the Known and Potential Risks and Benefits of Voxelotor

Clinical data to date have shown that treatment with voxelotor results in a dose-dependent increase in Hb within 2 weeks that is maintained through 24 weeks, and with an associated decrease in clinical measures of hemolysis which correlates with drug exposure (Brown, 2018; Vichinsky, 2018). In a global, multicenter, Phase 3, double-blind, randomized, placebo-controlled trial of voxelotor in participants with SCD (Study GBT440-031), the percentage of participants achieving an Hb response (> 1 g/dL Hb increase from Baseline at Week 24) was dose dependent: 51.1% for the voxelotor 1500 mg group, 32.6% for the voxelotor 900 mg group, and 6.5% for the placebo group ($p < 0.001$ for each voxelotor dose vs placebo). In the 1500 mg group, the mean Hb increase at Week 24 was 1.14 g/dL and in placebo -0.08 g/dL. Consistent with the improvement in Hb, the reductions in hemolysis measures (indirect bilirubin, absolute reticulocytes, percent reticulocytes, and LDH) were observed with both voxelotor 1500 mg and 900 mg compared to placebo. These were significant for indirect bilirubin (-25.9%, $p < 0.001$) and percent reticulocytes (-24.5%, $p < 0.001$) (Vichinsky, 2019).

Based on available data, voxelotor has been well tolerated in adult and adolescent patients with SCD. The most common adverse reactions in participants with SCD ≥ 12 years old in $\geq 10\%$ of participants treated with voxelotor 1500 mg with a difference of $> 3\%$ compared to placebo included headache, diarrhea, abdominal pain, nausea, fatigue, rash, and pyrexia. Other clinically relevant and less frequent adverse reactions included drug hypersensitivity ($< 1\%$). There were no reported events of anaphylaxis or anaphylactoid reactions in the clinical development program. The majority of treatment-emergent adverse events (TEAEs) were Grade 1 to Grade 2 in severity, clinically manageable, and reversed or resolved. Overall, the safety profile was similar in participants who were or were not receiving HU concomitantly, and between adults and adolescents. In SCD studies with voxelotor, the incidence of VOCs was similar to placebo

regardless of the extent of Hb increase with voxelotor. No increase in incidence of VOC was observed following voxelotor discontinuation. In study participants with SCD, there has been no evidence of mechanism-related toxicity (ie, inadequate O₂ offloading from voxelotor-bound Hb) as indicated by clinical observations, vital signs, electrocardiograms (ECGs), hematologic changes, or cardiopulmonary exercise testing (Howard, 2019; Stewart, 2018).

Overall, no concerning safety findings have been identified in studies with voxelotor and there has been no pattern of adverse events (AEs) that would raise concerns or alter the benefit-risk profile of voxelotor.

Additional information regarding safety is available in the Voxelotor IB (provided separately).

1.5. Description of and Justification for the Route of Administration, Dosage, Dosage Regimen, and Treatment Period(s)

[figure not shown]
Voxelotor is available in an oral form and is intended for once daily administration. See below, and Section 3.2 and Section 5.1 for additional information regarding the dose to be used in this study.

1.5.1. Study Rationale

In the pivotal Phase 3 Study GBT440-031, voxelotor was shown to have a dose-dependent (1500 mg > 900 mg orally daily), and clinically meaningful increase in Hb, as well as concurrent reductions in clinical measures of hemolysis. Study GBT440-029, is designed to assess tolerability, safety, and PD of voxelotor dose levels higher than 1500 mg daily (the maximum dose in the pivotal Phase 3 study) and to compare these results to the 1500 mg dose. The rationale for this study is based on an exposure-response analysis from the pivotal Study GBT440-031, which showed a linear relationship between whole blood voxelotor and %Hb occupancy and efficacy as measured by improvement in Hb (see Figure 1 below) and hemolysis markers. The 1500 mg dose led to a mean Hb occupancy of 29% and led to a mean Hb increase of 1.1 g/dL. At 3000 mg of voxelotor, assuming a linear relationship, the mean Hb occupancy is projected to be 49.3% with a Hb increase of 2.04 g/dL. Furthermore, no dose level has been associated with exposure-related concerning safety signals, and a maximum tolerated dose (MTD) has not been defined. Treatment-related AEs were mostly grade 1/grade 2 gastrointestinal events. Given the predicted improved efficacy of higher doses, and lack of dose-limiting safety concerns, this study will investigate the potential for a greater benefit/risk for higher doses in patients with SCD.

In this study, baseline response will be characterized in participants receiving a 3-week treatment regimen with voxelotor 1500 mg and compared, within and across participants, to the response with the highest dose level tolerated at steady state. Dose escalation will be done in 3-week increments to assess tolerability at the escalated dose.

Figure 1: Relationships Between Change from Baseline in Hemoglobin at Week 24 and Percent Hemoglobin Occupancy

pkpd-wk24-hgb-20190508.pdf

C_{min} , minimum plasma concentration at steady state; CFB, change from baseline; Hb, hemoglobin.

Note: The vertical dashed lines indicate the median of % Hb occupancy for each dose group. The box plots describe the distribution of % Hb occupancy in each dose group. The left and right edges of the box correspond to the 25th and 75th percentiles, and the vertical line inside the box indicates the median. The solid blue line and gray shaded area represent a second-degree polynomial regression and 95% confidence interval through the data. The p-value for the polynomial relationship compared with the null model (no relationship) is shown on the plot. The black dashed line is a linear regression line through the data.

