3.2. Study Design

This is an open-label, sequential period, within-participant dose escalation study. Up to 40 participants with SCD (HbSS or HbSB⁰) who are 18 to $<$ 60 years of age, inclusive, will be enrolled.

Study participants will undergo up to four periods of voxelotor administration at progressively higher dose levels from 1500 mg until either a MTD or 3000 mg daily dose is reached, whichever occurs first ([Figure 2](#)):

- Period 1: 1500 mg per day: 1500 mg once daily (3×500 mg tablets) for 3 weeks (± 3 days)
- Period 2: 2000 mg per day: 1000 mg (2×500 mg) BID for 3 weeks (± 3 days)
- Period 3: 2500 mg per day: 1500 mg (3×500 mg) in morning and 1000 mg (2×500 mg) in evening daily for 3 weeks (± 3 days)
- Period 4: 3000 mg per day: 1500 mg (3×500 mg) BID for 3 weeks (± 3 days)
- Observation Period: MTD or 3000 mg daily for 24 weeks
- Safety Follow-up Period: from day of last dose to 28 days postdose.

[figure not shown]
If at any time a dose level $>$ 1500 mg is not tolerated by a participant in the dose escalation period, the dose may be reduced to a previous level for the participant, which will then be administered for 24 additional consecutive weeks as an observation period. Dose modifications are allowed during the observation period in consultation with the Sponsor's Medical Monitor ([Appendix C](#)).

If 1500 mg daily is the MTD for a participant, then the participant may enter the observation period and continue to receive 1500 mg, for up to 24 weeks or until they are able to roll over into the open-label extension or receive commercial voxelotor, where available. If the participant discontinues early from the study, the participant will undergo an End of Study (EOS) visit approximately 28 days after the last dose and will not be eligible for the open-label extension study.

The safety of study participants will be closely monitored by the study team. In addition, a Safety Monitoring Committee (SMC) will review safety, tolerability, and available PK and PD data at regular intervals (Section [3.4](#)). Blood draws for PK and PD (including Hb and hemolysis markers), routine chemistry and hematology laboratory tests, and 12-lead ECGs in triplicate will be obtained periodically, as listed in the Schedule of Assessments ([Appendix A](#), [Appendix B](#)).

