3.7.3. Early Discontinuation of Individual Participants

3.7.3.1. Individual Dose-limiting Toxicity Definition: Dose Escalation Period

Criteria for individual dose-limiting toxicity at doses beyond 1500 mg/day include, but are not limited to, the following:

- Any AE Grade ≥ 3 not clearly resulting from the underlying disease and deemed by the Investigator and/or Medical Monitor to be related to study drug.
- Worsening of an ongoing, treatment-related AE by ≥ 1 grade as per Investigator assessment
- Grade 3 nausea, vomiting, or diarrhea (deemed related to study drug) requiring hospitalization and/or intravenous fluids and parenteral tube feeding, total parenteral nutrition
- Study drug-related SAE

If any of these criteria is met, the Investigator should consider temporary dose reduction and/or study drug discontinuation for the individual participant after discussing with the Sponsor. If a subject discontinues early due to AEs, the subject will not be eligible for the open-label extension study.

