9.2. Adverse Event Reporting

9.2.1. General

All AEs will be recorded from the time the study participant signs the ICF until 28 days after the last dose of study drug. After this period, the Investigator should report only SAEs that are assessed as related to study drug until the EOS visit occurs. All SAEs must be reported within 24 hours of SAE awareness on the AE CRF via the electronic data capture (EDC) system. The Investigator is responsible for evaluating all AEs, obtaining supporting documents, and ensuring documentation of the event is complete. Details of each reported AE must include at minimum severity, relationship to study drug, duration and outcome. All (both serious and nonserious) AEs must be followed until they are resolved or stabilized, or until reasonable attempts to determine resolution of the event are exhausted.

Any participant who experiences an AE may be discontinued from study drug at any time at the discretion of the Investigator. The Sponsor and the CRO's Medical Monitors must be notified of the study participant's discontinuation.

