10.4. Data Analysis

Data will be presented by maximum dose level.

A TEAE, defined as an event that occurs on or after Day 1 of study drug or the worsening of a pre-existing condition on or after Day 1 of study drug, will be classified according to the Medical Dictionary for Regulatory Activities (MedDRA). The incidence of TEAEs and relatedness to study drug, as assessed by the Investigator, will be summarized descriptively by maximum dose level tolerated.

Clinical laboratory tests, ECGs, and vital signs over time will be summarized by maximum dose level tolerated using descriptive statistics. Change from baseline in ECG intervals will be evaluated using descriptive statistics. If an effect on mean change from baseline in QTc interval exceeding 10 msec is observed, concentration-QTc analysis may be explored. Results from the diagnostic interpretation will be summarized by maximum dose tolerated.

An Hb responder endpoint, defined as an increase in Hb of > 1 g/dL compared to Baseline, will be summarized. Additionally, change from baseline in hemoglobin and clinical measures of hemolysis (unconjugated bilirubin, % reticulocyte, absolute reticulocyte, and LDH) will be summarized by maximum dose level tolerated using descriptive statistics.

The incidence of VOCs will be summarized by maximum dose tolerated.

The CGI-C and PGI-C will be summarized by maximum dose level tolerated.

Population PK analysis using nonlinear mixed-effect modeling will be performed to characterize voxelotor PK in plasma, and whole blood.

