^f If positive urine test, serum pregnancy test will be done to confirm result.

^g Samples for hemoximetry will be obtained predose (within 30 minutes prior to dosing) at the investigational site.

^h Visits should take place in the morning. Participants are instructed to hold study drug until a predose blood sample for PK is obtained at the investigational site.

ⁱ During the observation period, the participant will receive their maximum tolerated dose or 3000 mg daily.

^j During the observation period, blood samples for PK will be obtained predose (within 30 minutes prior to dosing) at the investigational site.

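### Dose failures during the 24-week observation period are not counted as such, and the undefined grouping by maximum dose level tolerated leaves their effect on a participant's label open

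*Combined protocol and SAP*

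**What the plan says.** - **Objective and endpoints.** Section 2.1 makes tolerability and safety above 1500 mg the primary objective. Section 10.1.1 gives TEAEs and SAEs as the primary endpoints. Nothing in 10.1.1 to 10.1.3 measures dose reduction, hold or discontinuation.
- **Escalation.** Section 1.5.1: "Dose escalation will be done in 3-week increments to assess tolerability at the escalated dose". Section 3.7.3.1 is headed "Individual Dose-limiting Toxicity Definition: Dose Escalation Period". The rule in Section 3.2 for stepping down from a dose that is not tolerated is also limited to the escalation period. The synopsis version of that rule has no such limit.
- **Observation.** Section 3.2: "Observation Period: MTD or 3000 mg daily for 24 weeks". Appendix B, footnote i: "During the observation period, the participant will receive their maximum tolerated dose or 3000 mg daily". The synopsis and Section 3.2 both add: "Dose modifications are allowed during the observation period in consultation with the" Sponsor's Medical Monitor. Section 3.2 refers to Appendix C for this, and Appendix C names lack of tolerability among its triggers.
- **Analysis.** Section 10.4: "The incidence of TEAEs and relatedness to study drug, as assessed by the Investigator, will be summarized descriptively by maximum dose level tolerated". Laboratory tests, ECGs, vital signs, Hb change, hemolysis measures, VOCs, CGI-C and PGI-C use the same grouping. The section's opening sentence instead uses maximum dose level, without the word tolerated. Neither term is defined, and nor are the individual or study-level MTD.
- **AE record.** Section 9.2.1: "Details of each reported AE must include at minimum severity, relationship to study drug, duration and outcome".

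**The concern.** Beyond the escalation steps, what the observation period adds to the primary question is evidence on whether a dose that was acceptable for 3 weeks can be sustained. The plan gathers the events but does not say how a dose abandoned in that period is classified or reported. A participant may complete 3 weeks at 3000 mg and be reduced early in observation. No text says whether that person's maximum dose level tolerated is still 3000 mg. The study is open-label and the choice could be made after the data are seen. It affects nearly every table, including the tolerability result and the Hb result at the top dose.

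**Working it through.** **1. The plan's own timeline.** Section 3.6: 30 + 4 × 21 + 168 + 28 = 310 days, and 310/7 = 44.3 weeks. This agrees with the stated maximum of 44 weeks.

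**2. Time at 3000 mg covered by the dose-limiting definition.** Period 4 lasts 3 weeks and observation 24 weeks. 3/(3 + 24) = 11.1% is inside and 24/27 = 88.9% is outside. With the ±3-day window the inside share runs from 18/(18 + 168) = 9.7% to 24/(24 + 168) = 12.5%.

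**3. The two readings of the label.** Take a participant who completes Period 4, is reduced at the end of observation Week 2 and stays at the lower dose. Time at 3000 mg is 3 + 2 = 5 weeks, and 24 − 2 = 22 observation weeks follow at a lower dose.

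- *Label stays at the highest level reached.* The AEs, Hb values and VOCs of those 22 weeks are credited to 3000 mg.
- *Label is revised down.* The event that ended 3000 mg is tabulated under a lower dose, and the 3000 mg column keeps only those who could stay on it.

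Neither table gives the number who started 3000 mg and could remain on it.

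**4. Possible size.** The documents give no failure rate, so every risk and hazard shape here is an assumption. Let p be the 3-week failure risk, and consider those who enter observation at that dose.

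- Constant hazard: observation is eight further 3-week blocks, so the risk is 1 − (1 − p)^8.
- Front-loaded hazard (Weibull, shape 0.5): cumulative hazard grows with the square root of time. √(27/3) − 1 = 2, so the risk is 1 − (1 − p)^2.

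| Assumed p | Front-loaded | Constant |
|---|---|---|
| 3% | 6% | 22% |
| 5% | 10% | 34% |
| 10% | 19% | 57% |

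Viewed the other way, suppose 10% to 50% fail over 27 weeks. The share of failures falling after the 3-week step is then 88% at most (constant hazard, 10% failing) and 59% at least (shape 0.5, 50% failing).

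**5. Hb, for illustration only.** Section 1.5.1 projects 1.1 g/dL at 1500 mg and 2.04 g/dL at 3000 mg. (2.04 − 1.1)/3 = 0.313 g/dL per 500 mg. If every failure were a lasting one-level reduction, the Week 24 mean in a 3000 mg group defined by highest level reached would fall as follows:

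- Front-loaded: 0.06 × 0.313 = 0.02 to 0.19 × 0.313 = 0.06 g/dL, which is 2% to 6% of the projected 0.94 g/dL gain.
- Constant: 0.22 × 0.313 = 0.07 to 0.57 × 0.313 = 0.18 g/dL, which is 7% to 19%.

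Appendix C allows return to the original dose, so lasting reductions in every case is an extreme assumption.

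**The case against.** The strongest reply is that observation-period failures are already measured. TEAEs count from Day 1 with no cut-off at the end of escalation, AEs are collected to 28 days after the last dose, and the Safety Monitoring Committee reviews tolerability throughout. This stands. A reader might infer that such a failure is no tolerability outcome at all, but the documents do not support that: the event behind it is part of the primary endpoint. What is missing is a count of the dose failure itself. Committee oversight is not a reported estimate.

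A reader might also infer that the label is fixed on entry to observation and that the reported tolerated dose is therefore biased upward. The documents do not establish this. Footnote i of Appendix B says what dose is given, not how participants are classified. The synopsis rule is not limited to escalation, and the list of dose-limiting criteria in 3.7.3.1 is open-ended. The opposite reading is possible, so the direction of any distortion is not settled.

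On the AE record, Section 9.2.1 sets a minimum, the case report form is not in the documents, and Section 11.2 requires treatment administration to be recorded. Action taken may well be collected, but the text does not require it.

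Finally, the study is descriptive, with up to 40 participants. A Kaplan-Meier curve for every dose level would be a poor remedy, because participants who tolerate 2000 or 2500 mg leave that level at Week 3 by design. This also stands, and it limits the fix.

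**Conclusion.** The point holds as a gap in definition and reporting. Tolerability above 1500 mg is the primary objective, yet 24 of the 27 planned weeks at 3000 mg lie outside the dose-limiting definition. No endpoint counts dose failures in those weeks, and the grouping variable is undefined. Under either reading some data are attributed to the wrong dose. The text leaves open that a dose abandoned in observation is reported as tolerated, but does not prescribe it.

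The size cannot be derived from the documents. Observation-period failure of 6% to 19% (front-loaded) or 22% to 57% (constant hazard) rests on assumed 3-week risks of 3% to 10%, and the Hb figures on the further assumption of lasting one-level reductions. The sponsor should correct this, chiefly because it affects how the primary result is read and the needed dosing data are already kept.

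**What to change.** In Section 10.4 and the synopsis:

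1. Define maximum dose level tolerated, use one term throughout, and state how observation-period reductions, holds and discontinuations affect it.
2. For each dose level, among all who started it, tabulate the number and percentage with AE-related reduction, hold or discontinuation, separately for the 3-week step and the observation period. Add a time-to-event summary only for the level carried into observation.
3. Tabulate TEAEs by dose at onset. Show observation-period Hb and hemolysis measures by dose taken at the visit, alongside the summary by entry dose, noting that dose at visit is a post-treatment variable.

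In Section 9.2.1, require action taken with study drug for each AE. Reconcile the non-tolerance wording in the synopsis (Study Design) with that in Section 3.2.

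The cost is protocol and analysis wording, a few more tables and, if not already collected, one AE form field. Treatment administration (11.2) and tablet counts (Section 7) are already recorded. Reported tolerability may look less favourable. No change to dosing or patient management is proposed.
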